- To determine the safety and toxicity, and progression-free interval (PFI) of LY2606368 in pretreated participants.
- To determine biochemical changes in the DNA damage repair and cell cycle check point pathways in tumor and blood samples in response to treatment.
- To determine potential resistance mechanisms to LY2606368 treatment in HGSOC.

Eligibility:

- Participants with recurrent/refractory BRCA mutant breast or ovarian cancer, HGSOC, and TNBC, for whom there remains no standard curative measures.
- A documented deleterious germline or somatic BRCA mutation for breast or ovarian cancer participants enrolling in Cohort 1.
- Negative BRCA mutation testing or negative family history of hereditary breast and ovarian cancer syndrome for HGSOC (Cohort 2).
- Negative BRCA mutation testing or negative family history of hereditary breast and ovarian cancer syndrome for TNBC (Cohort 3).
- Effective with amendment I (version date 4/24/2017), mCRPC, Cohort 4 was closed.
- Negative BRCA mutation testing or negative family history of hereditary breast and ovarian cancer syndrome for recurrent platinum-resistant HGSOC with measurable and biopsiable disease (Cohort 5).
- Negative BRCA mutation testing or negative family history of hereditary breast and ovarian cancer syndrome for recurrent platinum-resistant HGSOC with measurable but *without* biopsiable disease (Cohort 6).

CC Protocol #: 14-C-0156

Abbreviated Title: LY Chk1/2 Inhibitor

Amendment Version Date: 12/02/2020

- Participants must be off prior chemotherapy, radiation therapy, hormonal therapy, or biological therapy for at least 4 weeks.
- ECOG performance status 0-2 and adequate organ and marrow function.

Design:

- This is an open label, single arm phase II trial to examine activity of LY2606368 in participants in the 6 independent cohorts (Cohorts 1-6).
- LY2606368 will be dosed at the RP2D of 105 mg/m² IV once every 14 days of a 28day-cycle.
- Research samples including whole blood, CTCs, and tumor biopsies will be obtained for PD endpoints at baseline, Cycle 1 Day 15 (6-24hr post-2nd dose), and/or at progression in all participants. Tumor biopsies will not be performed in Cohort 6.
- Participants (Cohorts 1-3, 5 and 6) will be evaluated every two cycles for response using RECIST v1.1 and every cycle for safety using CTCAE v4.0.

TABLE OF CONTENTS

STUDY SCHEMA	2
PRÉCIS	3
TABLE OF CONTENTS	5
STATEMENT OF COMPLIANCE	8
1. INTRODUCTION	8
1.1 Study Objectives	8
1.1.1 Primary Objective:	8

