1. INTRODUCTION

1.1 STUDY OBJECTIVES

1.1.1 Primary Objective:

- To determine the objective response rate (CR+PR) of single agent LY2606368, a second-generation Chk 1/2 inhibitor, in participants with BRCA mutation-associated breast and ovarian cancers, HGSOC and TNBC at low genetic risk.

1.1.2 Secondary Objectives:

- To determine the safety and toxicity of LY2606368 in pretreated participants.
- To determine the progression-free interval (PFI) of the response to LY2606368
- To investigate response and resistance mechanisms of LY2606368 in recurrent platinum-resistant HGSOC participants.

1.1.3 Exploratory Objectives:

- To determine biochemical changes in the DNA damage repair and cell cycle check point pathways in tumor and blood samples in response to treatment.
- To investigate potential predictive biomarkers to Chk1/2 inhibitor in participants.
- To confirm the efficacy of LY2606368 in recurrent HGSOC participants by independent central review.

CC Protocol #: 14-C-0156

Abbreviated Title: LY Chk1/2 Inhibitor

Amendment Version Date: 12/02/2020

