6.3.1 Definitions

Evaluable for toxicity: All participants will be evaluable for toxicity from the time of their first treatment with LY2606368.

Evaluable for objective response: Only those participants who have measurable disease present at baseline, have received at least one cycle of therapy, and have had their disease re-evaluated will be considered evaluable for response. These participants will have their response classified according to the definitions stated below. (Note: Participants who exhibit objective disease progression prior to the end of cycle 1 will also be considered evaluable.)

Evaluable Non-Target Disease Response: Participants who have lesions present at baseline that are evaluable but do not meet the definitions of measurable disease, have received at least one cycle of therapy, and have had their disease re-evaluated will be considered evaluable for non-target disease. The response assessment is based on the presence, absence, or unequivocal progression of the lesions.

CC Protocol #: 14-C-0156
Abbreviated Title: LY Chk1/2 Inhibitor
Amendment Version Date: 12/02/2020

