6.3.4.3 Evaluation of Best Overall Response

The best overall response is the best response recorded from the start of the treatment until disease progression/recurrence (taking as reference for progressive disease the smallest measurements recorded since the treatment started). The participant's best response assignment will depend on the achievement of both measurement and confirmation criteria.

CC Protocol #: 14-C-0156

Abbreviated Title: LY Chk1/2 Inhibitor

Amendment Version Date: 12/02/2020

For Participants with Measurable Disease (i.e., Target Disease)

Target Lesions	Non-Target Lesions	New Lesions	Overall Response	Best Overall Response when Confirmation is Required*
CR	CR	No	CR	≥ 4 wks. Confirmation**
CR	Non-CR/Non-PD	No	PR	
CR	Not evaluated	No	PR	
PR	Non-CR/Non-PD/not evaluated	No	PR	≥ 4 wks. Confirmation**
SD	Non-CR/Non-PD/not evaluated	No	SD	Documented at least once ≥ 4 wks. from baseline**
PD	Any	Yes or No	PD	
Any	PD***	Yes or No	PD	no prior SD, PR or CR
Any	Any	Yes	PD	

* See RECIST 1.1 manuscript for further details on what is evidence of a new lesion.
 ** Only for non-randomized trials with response as primary endpoint.
 *** In exceptional circumstances, unequivocal progression in non-target lesions may be accepted as disease progression.
Note: Participants with a global deterioration of health status requiring discontinuation of treatment without objective evidence of disease progression at that time should be reported as "symptomatic deterioration." Every effort should be made to document the objective progression even after discontinuation of treatment.

For Participants with Non-Measurable Disease (i.e., Non-Target Disease)

Non-Target Lesions	New Lesions	Overall Response
--------------------	-------------	------------------

CC Protocol #: 14-C-0156

Abbreviated Title: LY Chk1/2 Inhibitor

Amendment Version Date: 12/02/2020

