evaluable participants to describe the results obtained. If there are 11 (or more) responders out of 35 evaluable participants (31.4%), the exact two-sided 95% confidence interval about the proportion responding extends from 16.9% to 49.3%, thus ruling out 15% and demonstrating consistency with a result of at least 40%. An early stopping rule also will be implemented as follows: if after 10 evaluable participants have been enrolled, there are 0 to 1 responders, then no further participants will be accrued since the upper one-sided 90% confidence bound on 1/10 is 0.337. This would mean that there is a reasonably high probability that the true response rate is below 1/3, obtained previously, and thus the results may not be as promising as expected.

The primary analyses will be done separately by disease cohort, although the response rates may not differ substantially by type of disease. In addition, if results are sufficiently similar, the participants from all four-disease types may be evaluated together in a single cohort in an exploratory fashion. In each cohort, participants will be divided into groups based on whether they responded (PR+CR) or not, or experienced at least some clinical benefit (CR+PR+SD) or not, and when any biologic or biochemical parameters are obtained, the changes in these parameters from baseline will be compared between the two groups using a Wilcoxon rank sum test. As these will be considered exploratory analyses, the results will not be adjusted for any multiple comparisons but will be considered in the context of the hypothesis generating nature of the evaluations. PFI will be estimated using a Kaplan-Meier curve based on all evaluable participants, as well as separately by cohort. The PFI at selected points will also be reported, along with associated 80% and 95% confidence intervals. Safety and toxicity in this population will be determined by tabulating the toxicity grades identified in the participants treated on the trial, by cohort, and describing the findings as needed.

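### PFI is planned in evaluable rather than all treated participants, and the plan does not say whether death is an event

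*Combined protocol and SAP*

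**What the plan says.** PFI is a secondary endpoint. Three places describe it:

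- Précis, Objectives: "progression-free interval (PFI) of LY2606368 in pretreated participants".
- Section 1.1.2: "To determine the progression-free interval (PFI) of the response to LY2606368".
- Section 10: "PFI will be estimated using a Kaplan-Meier curve based on all evaluable participants, as well as separately by cohort", followed by "The PFI at selected points will also be reported, along with associated 80% and 95% confidence intervals".

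None of them, and no other section, gives a time origin, an event definition, a censoring rule or the handling of death for PFI. Section 6.3.5 defines duration of response and duration of stable disease. Both end at progression, but neither is called PFI.

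Section 6.3.1 gives evaluable more than one meaning. For response, participants need measurable disease at baseline and must "have received at least one cycle of therapy, and have had their disease re-evaluated will be considered evaluable for response". A note adds: "Participants who exhibit objective disease progression prior to the end of cycle 1 will also be considered evaluable". For toxicity the set is everyone treated: "All participants will be evaluable for toxicity from the time of their first treatment with LY2606368". Section 10 does not say which meaning governs PFI.

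**The concern.** A time-to-event curve can include every participant from the first dose; those with no scan contribute an event or a censoring time. Requiring a re-evaluation means that a participant must get as far as being assessed before being counted. In a heavily pretreated population, some of those who do not get that far will have died or deteriorated, and they are the shortest intervals. Dropping them tends to push the curve up.

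The silence on death works the same way if it is resolved by censoring: a death without documented progression would then be treated as if that participant's later course were like that of participants still at risk. Two analysts could follow this plan faithfully and report different PFI values. Section 1.2 says that efficacy data from these cohorts are meant to come before a randomized phase 2/3 trial, so the figures may be carried forward.

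**Working it through.** The documents give no expected PFI, event count or power for it, so there is no PFI figure to reproduce. The check has four steps.

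**1. Which evaluable set applies.** Section 10 uses the word throughout for the denominator of the response rate (9, 36 and 35 evaluable participants, and 10 at the early looks in cohorts 5 and 6). It allows for a small number of non-evaluable participants in the accrual ceiling, and it tabulates toxicity in those treated, without the word evaluable. All of this points to the response definition.

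**2. Who would be missing.** Under the response definition with its note:

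- Objective progression before the end of cycle 1: kept.
- Progression found on a re-evaluation scan: kept.
- Death, or clinical deterioration without objective progression, before re-evaluation: left out. With 28-day cycles and the first scheduled scan at Cycle 3 Day 1 (Section 3.4), this window can last about 2 × 28 = 56 days.
- Stopping for toxicity or withdrawal before re-evaluation: left out, but some of these would only be censored in an all-treated curve.

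Section 6.3.4.3 has a reporting category for "Participants with a global deterioration of health status requiring discontinuation of treatment without objective evidence of disease progression at that time", but does not say how it enters PFI.

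**3. Size of the exclusion.** Inputs from Section 10: 3 × 24 + 36 + 35 = 143 evaluable, which matches the stated total; the ceiling is 153. The allowance is 153 − 143 = 10, and x = 10/153 = 6.5%. As a worst case, assume that all ten are early failures. Then

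S_all(t) = (1 − x) × S_evaluable(t), with 1 − x = 143/153 = 0.935.

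| Progression-free, evaluable | Progression-free, all treated |
|---|---|
| 75% | 70.1% |
| 50% | 46.7% |
| 25% | 23.4% |

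For the median, assume an exponential curve in the evaluable set. Setting (1 − x) × exp(−λt) = 0.5 gives t = ln(2(1 − x))/λ, against a reported median of ln 2/λ. The ratio is ln(2 × 0.935)/ln 2 = 0.90. An assumed reported median of 6.0 months becomes 5.4 months.

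**4. Size of the death question.** Let d be the share of events that are deaths without progression (an assumption; the documents give none). With proportional cause-specific hazards, a curve that censors deaths equals S_composite^(1 − d). A composite value of 50% would read:

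- d = 5%: 0.5^0.95 = 51.8%
- d = 10%: 0.5^0.90 = 53.6%
- d = 20%: 0.5^0.80 = 57.4%

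This applies only if deaths are in fact censored.

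**The case against.** The strongest reply is that the plan is less selective than it looks. Early objective progressors are expressly kept by the note in Section 6.3.1. Section 3.2 allows earlier imaging when there are signs of clinical progression, and Section 6.3.4.3 asks for every effort to document progression after treatment stops for deterioration. Evaluable could also mean evaluable for toxicity, in which case no treated participant is lost. PFI carries no hypothesis or decision rule, and Section 5.3.1 describes the study as mainly a pilot. Most of this stands, and it is why the effect is probably small. It does not remove the gap for death or undocumented deterioration before re-evaluation, and the usage in Section 10 makes the toxicity meaning the less likely one.

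Four stronger readings are tempting, and the documents do not support them:

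- *Deaths are not counted.* The plan is silent on death in PFI. Only the durations in Section 6.3.5 end at progression alone, and they do not define PFI.
- *Early failures as a group are left out.* Only those without objective progression are at risk of exclusion.
- *PFI might be measured from response, so that two endpoints share one name.* A curve in all evaluable participants cannot start at response, because non-responders have no response date. The précis agrees with Section 10, and duration of response has its own definition. The phrase in Section 1.1.2 is best read as loose wording.
- *Up to 20% could be excluded, from the interim 20 evaluable of 25 in cohort 2 (Section 1.2).* That is an interim count from one cohort, with some responses still ongoing. The other five may simply not have been assessed yet, so the fraction bounds nothing.

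**Conclusion.** The point holds as a matter of analysis set and event definition for a secondary, descriptive endpoint. On its most natural reading, Section 10 leaves treated participants who die or deteriorate before re-evaluation, without documented progression, out of the PFI curve, and it does not settle whether death is an event. The exclusion tends to lengthen PFI, and censoring deaths would do the same.

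The actual size cannot be known from the documents. At the plan's own allowance, the exclusion costs at most 3.3 points at a 50% progression-free value, or about 10% of the median. Those limits assume that all ten non-evaluable participants are early failures and, for the median, that the curve is exponential. They refer to the pooled curve; a single cohort could differ. The death figures are illustrations over assumed shares. No PFI figure in the documents is shown to be wrong, and the primary response-rate analysis is not touched.

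**What to change.** In Section 10, define PFI once: time from Cycle 1 Day 1 to RECIST 1.1 progression or death from any cause, in all participants who received LY2606368, by Kaplan-Meier overall and by cohort. State the censoring rule, including the start of another anti-cancer therapy (an off-study criterion in Section 3.6.2) and the handling of symptomatic deterioration without documented progression.

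In Section 1.1.2, delete 'of the response' so that the objective agrees with the précis and Section 10. Report duration of response, as defined in Section 6.3.5, separately for responders.

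The cost is a few sentences in two sections. No new assessments are needed beyond recording the dates of progression, death and new therapy. The downside is that reported PFI may be slightly shorter.

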11 COLLABORATIVE AGREEMENTS

11.1 COOPERATIVE RESEARCH AND DEVELOPMENT AGREEMENT (CRADA)

11.1.1 Eli Lilly and Company

The investigational study agent, LY2606368, is provided by Eli Lilly and Company under a Collaborative Agreement [Cooperative Research and Development Agreement (CRADA #02915)].

12 HUMAN SUBJECTS PROTECTIONS

12.1 RATIONALE FOR SUBJECT SELECTION

Subjects from all racial/ethnic groups are eligible for this study if they meet the eligibility criteria. To date, there is no information that suggests that differences in drug metabolism or disease response would be expected in one group compared to another. Efforts will be made to extend accrual to a representative population, but in this preliminary study, a balance must be struck between patient safety considerations and limitations on the number of individuals exposed to potentially toxic and/or ineffective treatments on the one hand and the need to explore ethnic aspects of clinical research on the other hand. If differences in outcome that correlate to ethnic identity are noted, accrual may be expanded or a follow-up study may be written to investigate those differences more fully. This study will be recruited through internal referral, our local physician referral base, and through Cancer Hotline information.

12.2 PARTICIPATION OF CHILDREN

Subjects under 18 are excluded because the incidence of breast or ovarian cancer in this population is extremely rare. The study medication is also investigational and has not been studied in pediatric populations.

12.3 PARTICIPATION OF SUBJECTS UNABLE TO GIVE CONSENT

Adults unable to provide consent are excluded from enrolling in the protocol. However, it is possible that subjects enrolled in the protocol may permanently lose the capacity to consent for themselves during the course of this study. In the event this occurs, the subjects will remain in the study because, although the risk of participation is greater than minimal due to the potential toxicities of treatment, there is a prospect for direct benefit due to the potential for reduction of tumor burden. All subjects \geq age 18 will be offered the opportunity to fill in their wishes for research and care, and assign a substitute decision maker on the "NIH Advance Directive for Health Care and Medical Research Participation" form so that another person can make decisions about their medical care in the event that they become incapacitated or cognitively impaired during the course of the study.

CC Protocol #: 14-C-0156

Abbreviated Title: LY Chk1/2 Inhibitor

Amendment Version Date: 12/02/2020

Note: The PI or AI will contact the NIH Ability to Consent Assessment Team (ACAT) for evaluation to assess ongoing capacity of the subjects and to identify an LAR, as needed.

Please see section **12.6.1** for consent procedure.

12.4 EVALUATION OF BENEFITS AND RISKS/DISCOMFORTS

Subjects enrolled on this study may receive direct benefit from participating in this protocol. LY2606368 demonstrated inhibition of tumor growth in multiple-tumor xenograft models as a single agent and in combination with gemcitabine. LY2606368, formulated in Captisol® for intravenous (IV) administration, appears to have a high volume of distribution, which indicates a wide distribution into tissues and organs. The most common SAEs deemed related to LY2606368 treatment were hematologic toxicities or complications resulting from neutropenia, leucopenia, or thrombocytopenia.

12.4.1 Risks of Radiation

The study will involve radiation from the following sources:

- Up to 3 CT scans for the collection of biopsies
- Up to 7 CT scans per year for disease assessment

Subjects in this study may be exposed to approximately 10.1 rem. This amount is more than would be expected from everyday background radiation. Being exposed to excess radiation can increase the risk of cancer. The risk of getting cancer from the radiation exposure in this study is 1 out of 100 (1%) and of getting a fatal cancer is 0.5 out of 100 (0.5%).

CC Protocol #: 14-C-0156

Abbreviated Title: LY Chk1/2 Inhibitor

Amendment Version Date: 12/02/2020

12.4.2 Risk of Treatment: Details of the risk of drug therapy are detailed in section [13](#).

12.4.3 Blood draws: Side effects of blood draws include pain and bruising, lightheadedness, and rarely, fainting.

12.4.4 CT scans: In addition to the radiation risks discussed above, risks associated with CT scans are allergic reaction to and kidney damage from the contrast dye, nausea, vomiting, and anxiety.

12.4.5 Biopsies: The non-radiation risks associated with the biopsy procedure include pain, swelling and/or bleeding at the biopsy site; infection; and allergic reaction to the local anesthetic used.

12.5 RISKS/BENEFITS ANALYSIS

This dose and schedule of 105mg/m² was selected based on the nonclinical PK/PD model, the clinical PK data demonstrating that the LY2606368 systemic exposure at the Maximum Tolerated Dose (MTD) for each schedule of administration is in the range predicted for maximal tumor response, the human PD simulations that predict the average %pChk1 inhibition at the MTD for each schedule of administration achieves the requirements described for the minimum tumor response, the similar safety profile for each schedule, and the increased patient convenience.

- Adult subjects: More than minimal risk and the prospect of direct benefit.
- Adults unable to consent: Category B - Research involving greater than minimal risk but presenting the prospect of direct benefit to the individual subjects.
- Protocol Specific Justification for Risk Assessment: For adults who lose the capacity to consent the risk is greater than minimal due to the potential toxicities of treatment, but there is prospect for direct benefit due to the potential for reduction of tumor burden.

12.6 CONSENT PROCESS AND DOCUMENTATION

The informed consent document will be provided to the participant or consent designee(s) as applicable for review prior to consenting. A designated study investigator will carefully explain the procedures and tests involved in this study, and the associated risks, discomforts and benefits. In order to minimize potential coercion, as much time as is needed to review the document will be

CC Protocol #: 14-C-0156

Abbreviated Title: LY Chk1/2 Inhibitor

Amendment Version Date: 12/02/2020

given, including an opportunity to discuss it with friends, family members and/or other advisors, and to ask questions of any designated study investigator. A signed informed consent document will be obtained prior to entry onto the study.

The initial consent process as well as re-consent, when required, may take place in person or remotely (e.g., via telephone or other NIH approved remote platforms) per discretion of the designated study investigator and with the agreement of the participant/consent designee(s).

Whether in person or remote, the privacy of the subject will be maintained. Consenting investigators (and participant/consent designee, when in person) will be located in a private area (e.g., clinic consult room). When consent is conducted remotely, the participant/consent designee will be informed of the private nature of the discussion and will be encouraged to relocate to a more private setting if needed.

